9.4	RECORDS RETENTION	41
10	STUDY MONITORING, AUDITING, AND INSPECTING	41
10.1	STUDY MONITORING PLAN	41
10.2	AUDITING AND INSPECTING	42
11	ETHICAL CONSIDERATIONS.....	42
12	STUDY FINANCES.....	42
12.1	FUNDING SOURCE.....	42
12.2	CONFLICT OF INTEREST	42
13	PUBLICATION PLAN.....	43
14	REFERENCES.....	43
15	ATTACHMENTS	50
15.1	INVESTIGATIONAL DRUG BROCHURE FOR AIR001	ERROR! BOOKMARK NOT DEFINED.
15.2	CHARTER FOR DATA SAFETY AND MONITORING BOARD	ERROR! BOOKMARK NOT DEFINED.
15.3	SCHEDULE OF ASSESSMENTS	50

LIST OF ABBREVIATIONS

AE	Adverse Event/Adverse Experience
CFR	Code of Federal Regulations
CRF	Case Report Form
DSMB	Data and Safety Monitoring Board
FDA	Food and Drug Administration
GCP	Good Clinical Practice
HIPAA	Health Insurance Portability and Accountability Act
IB	Investigator's Brochure
ITT	Intent to Treat
IND	Investigational New Drug Application
IRB	Institutional Review Board
IP	Investigational Product
PHI	Protected Health Information
PI	Principal Investigator
SAE	Serious Adverse Event/Serious Adverse Experience
SOP	Standard Operating Procedure

Study Summary

Title	Inorganic Nitrite To Amplify the Benefits and Tolerability of Exercise Training In Heart Failure With Preserved Ejection Fraction
Protocol Number	16-001467
Phase	Phase II
Methodology	
This is a randomized, blinded, placebo-controlled, two-stage, parallel-group clinical trial with all subjects receiving exercise training (ET) and randomized to either inorganic sodium nitrite or matching placebo.
 
The trial includes 2 stages. In stage I, which has been completed, patients received inhaled nitrite/placebo. In stage II, patients will receive oral nitrite/placebo.

Overall Study Duration	4 years
Subject Participation Duration	14 weeks
Single or Multi-Site	Single site
Objectives	To determine if sodium nitrite can improve the clinical responses to ET in subjects with heart failure and preserved ejection fraction (HFpEF).
Number of Subjects	100 (36 received inhaled nitrite/placebo in the completed stage I, up to another 64 will receive oral nitrite/placebo in stage II of the study)

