Diagnosis and Main Inclusion Criteria	
Heart failure with preserved ejection fraction (HFpEF) defined by clinical heart failure, normal EF ($\geq 50\%$) and at least one of the following:
 
 • Previous hospitalization for HF with radiographic evidence (pulmonary venous hypertension, vascular congestion, interstitial edema, pleural effusion) of pulmonary congestion or • Catheterization documented elevated filling pressures at rest or with exercise or • Elevated NT-proBNP (>400 pg/ml) or • Echo evidence of diastolic dysfunction/elevated filling pressures manifest by medial E/e' ratio ≥ 15 and/or left atrial enlargement and chronic treatment with a loop diuretic for signs or symptoms of heart failure
Study Product, Dose, Route, Regimen	
Stage I tested Inhaled, nebulized sodium nitrite (AIR001) 80 mg at least 4 hours apart three times daily during waking hours (i.e. 08:00, 12:00, 16:00).
 
Stage II is testing oral nitrite 40 mg tid capsules vs matching placebo capsules (same dosing frequency).

Duration of Administration	12 weeks
Reference therapy	Placebo
Statistical Methodology	Data will be analyzed according to ITT principles (assigned group regardless of study drug administration or compliance with ET benchmarks achieved). Primary hypotheses will be tested using a two-sample t-test on the change (baseline to 12 week). Testing will be stratified by route of administration.

1 Introduction

Heart failure with preserved ejection fraction (HFpEF) afflicts millions of older Americans and is associated with exercise intolerance, reduced quality of life (QOL), high health care costs, and increased mortality. People with HFpEF display increased cardiac filling pressures and inadequate cardiac output reserve to deliver blood to the body during exercise. Numerous lines of evidence have implicated abnormalities in nitric oxide-cyclic guanosine monophosphate (NO- cGMP) signaling as playing a key role in promoting these abnormalities. While there is currently no proven effective medical treatment for HFpEF, exercise training (ET) has been shown to improve aerobic capacity and QOL in this population.

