Participants should be treated with standard HFpEF strategies (diuretics for congestion, blood pressure control and heart rate control if Participant is in atrial fibrillation) as per recommended guidelines. Participants should be on stable medications and with adequate blood pressure control prior to entry as outlined in the entry criteria. Further adjustment of diuretics or blood pressure medications during the study period is discouraged and should only be performed according to new and clinically compelling worsening of clinical status. As above, therapy with organic nitrates, phosphodiesterase-5 inhibitors or soluble guanylyl cyclase activators is contra- indicated during the study period.

Data for baseline medication usage will be obtained for descriptive purposes at Study Visit 1.

57 Packaging

The inhaled nitrite drug or matching placebo was supplied in one ml squeezable plastic ampules. The ampules are produced in snap-apart groups of 5 vials and are placed in a nitrogen filled pouch. Participants are instructed to open and utilize one pouch at a time. The medication is stable at room temperature.

The oral nitrite drug or matching placebo using in Stage II will be supplied in capsules compounded by The University of Iowa Pharmaceuticals, Iowa City, IA, then shipped to the Research pharmacy at the University of Pittsburgh according to specifications in the IND of [name] then stored and dispensed by the Research pharmacy at the Mayo Clinic.

58 Blinding of Study

Only research pharmacy staff will be aware of randomization scheme and all study personnel and subjects will remain blinded to the identity of study drug. Placebo and nitrite ampules (Stage I) and capsules (Stage II) have an identical appearance assuring maintenance of the blind.

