7.1 Statistical Overview

7.2 The full statistical details for this protocol are documented in the supplementary Statistical Analysis Plan (SAP). This protocol provides the key information, namely the justification for the sample size and the details on the primary analysis. The details regarding secondary endpoints, subgroup analyses, missing data and analysis sets are provided in the SAP. **Sample Size Determination**

In the RELAX trial, the mean \pm SD change in peak VO₂ with placebo in subjects with HFpEF treated for 6 months was 0 ± 2.0 ml/kg/min,³⁶ and in a previous trial of ET in HFpEF, the increase in peak VO in the ET arm was $+2.3\pm 2.2$ ml/kg/min.²² An increase of 75% (additional 1.5 ml/kg/min) in this change would be considered clinically relevant. Thus, we estimate that a sample size of N=34 participants per group will be required to provide 80% statistical power (two-tailed, alpha=0.05) to detect the difference of 1.5 ml/kg/min between subjects randomized to NO₂⁻ with ET versus placebo with ET. To account for attrition, we will increase our number of randomized subjects to 40/group (enroll 80 subjects total to accrue 68 total or 34 in each group).

Stage 1 was discontinued early because of loss of inhaled nitrite availability, therefore we will accrue a total of 68 patients with complete data combining the patients with complete data receiving inhaled placebo in Stage I (n=17) with another 51 patients in Stage II (17 receiving placebo and 34 receiving nitrite) to ensure that the study is adequately powered to test the study hypotheses.

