7.3 Primary Outcome Analysis

Primary Statistical Hypotheses:

H0: Change from baseline to 12 weeks in Peak VO₂ in participants randomized to NO₂⁻ will be equal to the change in Peak VO₂ in participants randomized to placebo.

Ha: The change from baseline to 12 weeks in Peak VO₂ will be different between the two randomized groups

Analysis Summary:

The primary statistical hypothesis will be tested using a regression framework. The dependent variable will be the change (baseline to 12 week) in Peak VO₂. An indicator variable will be used to indicate the randomized treatment assignment (NO₂⁻ vs. placebo as the referent). This analysis is equivalent to a two-sample t-test. While the study design is randomized, the number of participants is relatively small, so imbalance between putative confounding variables may be observed. To address this, we will conduct an a priori sensitivity analysis that will adjust for baseline Peak VO₂, BMI, Sex, and Age group strata through an extension of the regression model used for the primary analysis. The type III estimate of the treatment effect will be compared to the unadjusted estimate to assess the robustness of the randomization process.

Statistical testing for the primary analysis will be two-sided at the alpha=0.05 level of significance.

8 Safety and Adverse Events

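### Half of the planned placebo group in section 7.2 comes from Stage I, so the 34 v 34 primary test is partly an external-control comparison, its 80% power depends on those patients, and the Summary and section 7.3 disagree on how to analyse them

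*Combined protocol and SAP*

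**What the plan says.** - **Section 7.2 (sample size).** The plan asks for "80% statistical power (two-tailed, alpha=0.05) to detect the difference of 1.5 ml/kg/min" and concludes that "a sample size of N=34 participants per group will be required". After Stage I stopped early, it fills the two groups by "combining the patients with complete data receiving inhaled placebo in Stage I (n=17) with another 51 patients in Stage II". The 51 are 17 oral placebo and 34 oral nitrite. Section 1.0 gives the same plan, on the stated expectation that inhaled and oral placebo responses will not differ. It cites no data for this.
- **Study Summary, number of subjects.** "36 received inhaled nitrite/placebo in the completed stage I". The split by arm is not given there.
- **Study Summary, statistical methodology.** "Data will be analyzed according to ITT principles (assigned group regardless of study drug administration" or training compliance, with testing stratified by route.
- **Section 7.3.** The change in peak VO2 is regressed on one indicator for randomised treatment, described as equivalent to a two-sample t-test. "Statistical testing for the primary analysis will be two-sided at the alpha=0.05 level of significance". There is no stage or route term. The sensitivity model adds baseline peak VO2, BMI, sex and age group, but not stage.
- **Section 5.8.** "Placebo and nitrite ampules (Stage I) and capsules (Stage II) have an identical appearance assuring maintenance of the blind". The match is ampule to ampule and capsule to capsule.
- **Section 4.3.** Stage I patients may enter Stage II after at least 6 months, and data from the same patient in the two phases are to be analysed separately.
- **Section 7.1.** Analysis sets and missing data are deferred to a supplementary SAP. No SAP section defining them appears in the text reviewed.

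**The concern.** The 17 Stage I placebo patients were properly randomised and masked, but against inhaled nitrite. Against the oral nitrite group they are earlier, non-concurrent controls who used a nebuliser rather than a capsule. They are also counted because they have complete data, which sits awkwardly with ITT.

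The stages differ in more than the placebo. Study drug was taken immediately before training and the final exercise test in Stage I, and 30 minutes before in Stage II (sections 6.2 and 6.4). Home-based rehabilitation was offered from July 2020, which changes the background training itself. Anything that moves the mean change in peak VO2 between stages enters the treatment estimate through half of the control group and none of the nitrite group.

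At stake are the meaning of the primary result and its stated power. Read with section 7.3, the 34 v 34 test could be presented as a randomised, double-blind ITT comparison when only 34 v 17 of it is. Read with the Summary, the test is stratified by route and the 17 Stage I patients add nothing to the treatment contrast.

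**Working it through.** **Inputs.** From section 7.2: difference 1.5 ml/kg/min, 34 per group, two-sided alpha 0.05, 80% power. Two SDs are cited there: 2.0 (change on placebo in an earlier drug trial) and 2.2 (earlier training trial: "the increase in peak VO in the ET arm was" +2.3±2.2).

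**1. The plan's own figure.** n per group = 2 × (1.960 + 0.842)² × SD² / 1.5².
- SD 2.2: 2 × 7.849 × 4.84 / 2.25 = 33.8, so 34. This reproduces the plan.
- SD 2.0: 27.9, so 28. This does not.

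SD 2.2 is used below. With 34 v 34, SE = 2.2 × √(1/34 + 1/34) = 0.534. Power is 80.3% by the normal approximation and 79.1% by noncentral t.

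**2. Composition of the 68.**

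| | Inhaled (Stage I) | Oral (Stage II) | Total |
|---|---|---|---|
| Nitrite | 0 counted | 34 | 34 |
| Placebo | 17 | 17 | 34 |

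Non-concurrent share of controls: 17/34 = 50%. Stage I nitrite patients number at most 36 − 17 = 19 if the 17 lie within the 36. How many have complete data is not stated.

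**3. Test stratified by route (Summary) on this sample.** The inhaled row has no nitrite patients, so it yields no treatment contrast. What remains is 34 v 17: SE = 2.2 × √(1/34 + 1/17) = 0.653. Power is 63.1% (normal) or 61.4% (t). The difference detectable with 80% power is 2.80 × 0.653 = 1.83. At 2:1 allocation, 80% power for 1.5 would need 26 + 52 = 78 evaluable oral patients.

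**4. Unstratified test (section 7.3) on this sample.** If Stage I and Stage II placebo means differ by D, the pooled control mean moves by 17/34 × D, so the bias is D/2. The documents give no D, so these values are assumptions. Type I error is from simulated t-tests with no true effect and SD 2.2.

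| D (ml/kg/min) | Bias | Bias as share of 1.5 | Two-sided type I error |
|---|---|---|---|
| 0 | 0 | 0% | 5.0% |
| 0.25 | 0.125 | 8% | 5.6% |
| 0.5 | 0.25 | 17% | 7.3% |
| 1.0 | 0.5 | 33% | 14.6% |
| 1.5 | 0.75 | 50% | 26.3% |

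The bias can go either way. If Stage I placebo patients did better by 0.5 or 1.0, power for a true effect of 1.5 falls to 63.6% or 44.7%.

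**5. Both arms of both stages, contrasted within stage and combined by inverse variance.** This assumes m = 15 to 19 Stage I nitrite patients with complete data. Information in units of 1/SD² is 1/(1/17 + 1/34) + 1/(1/17 + 1/m). For m = 17 this is 11.33 + 8.50 = 19.83, so SE = 2.2/√19.83 = 0.494.
- Equal effect of 1.5 by both routes: power 84-86% (t) or 85-87% (normal) over m = 15 to 19.
- Inhaled effect nil, oral effect 1.5: Stage I carries 41-44% of the weight, the expected estimate is 0.88 to 0.84, and power is about 40-42%.

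**The case against.** A reader might infer that the Stage I nitrite data are thrown away. The documents do not say so. Section 7.2 sets an accrual target, not an analysis set; the Summary counts all 36 Stage I patients in its 100; and section 7.3 speaks of patients randomised to nitrite without naming a route. The promised stratification by route even makes best sense if Stage I nitrite is included. What stands is narrower: those patients are absent from the 68 that carry the power claim, and the three places cannot all describe the same comparison.

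A reader might also infer that both stages combined must be the primary analysis. That is a choice of estimand, not a correction. Dose, route and timing differ, and section 1.4 links the end of inhaled manufacture to a neutral trial result, so a small or absent inhaled effect is a live possibility. In that case the combination has less power than the oral comparison alone. Nor is Stage I a full-size completed comparison, since section 7.2 says it was discontinued early. Section 4.3 also bars joint analysis of a repeat participant's two phases.

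In the plan's favour, section 1.0 discloses the pooling and gives a reason, the trial has a single site, the endpoint is measured gas exchange, and treatment was returned to 12 weeks to match Stage I. If placebo responses are close, little harm follows: at D = 0.25 the type I error is 5.6%. These points make a large D less likely. They do not make the 17 randomised or masked against oral nitrite, and they do not remove the conflict over stratification.

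**Conclusion.** The point holds in this form. Half of the controls in the 34 v 34 comparison are non-concurrent, and the Summary and section 7.3 prescribe different tests for it. Stratified by route, the section 7.2 sample has about 61-63% power for 1.5 ml/kg/min. Pooled, it has 79-80%, but only by relying on an untested equality between stages, with bias D/2 and type I error from about 5.6% (D = 0.25) to 26% (D = 1.5).

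The power figures rest on SD 2.2, the only cited SD that reproduces 34 per group. The values of D are assumed. The material does not show that a stage difference exists, that the Stage I nitrite arm will go unreported, or that any particular primary analysis is required.

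**What to change.** Before unblinding:

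1. Reconcile the Summary, section 7.2 and section 7.3, and the SAP's analysis sets, on who is in the primary nitrite and placebo groups and whether the test is stratified by stage.
2. Report the randomised within-stage contrasts beside any pooled 34 v 34 result: Stage II oral (34 v 17), and Stage I inhaled nitrite v inhaled placebo.
3. Label the pooled result as partly external-control, and do not present it as a fully randomised, double-blind ITT comparison.
4. State in section 7.2 that 80% power depends on the 17 non-concurrent controls, against about 61-63% for the randomised oral comparison.

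The sponsor can choose the primary. Stage II alone keeps randomisation and a clear oral estimand at the lower power. A stage-stratified combination of both arms of both stages also keeps randomisation and has about 84-87% power if the effect is equal by route and 15-19 Stage I nitrite patients are evaluable, but about 40% if the inhaled effect is nil. It should show the route-specific effects and state how patients who took part in both stages are handled, so that section 4.3 is respected.

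The cost is wording in the Summary, sections 7.2 and 7.3 and the SAP, plus a rule for repeat participants. No data are needed beyond Stage I and the planned Stage II. The downside is that the oral-only randomised estimate is less precise and its stated power is lower.

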7.3 Primary Outcome Analysis

Primary Statistical Hypotheses:

H0: Change from baseline to 12 weeks in Peak VO₂ in participants randomized to NO₂⁻ will be equal to the change in Peak VO₂ in participants randomized to placebo.

Ha: The change from baseline to 12 weeks in Peak VO₂ will be different between the two randomized groups

Analysis Summary:

The primary statistical hypothesis will be tested using a regression framework. The dependent variable will be the change (baseline to 12 week) in Peak VO₂. An indicator variable will be used to indicate the randomized treatment assignment (NO₂⁻ vs. placebo as the referent). This analysis is equivalent to a two-sample t-test. While the study design is randomized, the number of participants is relatively small, so imbalance between putative confounding variables may be observed. To address this, we will conduct an a priori sensitivity analysis that will adjust for baseline Peak VO₂, BMI, Sex, and Age group strata through an extension of the regression model used for the primary analysis. The type III estimate of the treatment effect will be compared to the unadjusted estimate to assess the robustness of the randomization process.

Statistical testing for the primary analysis will be two-sided at the alpha=0.05 level of significance.

8 Safety and Adverse Events

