1.0 Summary of Protocol Changes and Rationale

Significant delays in obtaining study drug supply have forced us to make another modification to this study. In the last modification to the protocol two main changes were made: (1) we changed the route of administration of sodium nitrite from inhaled to oral, and (2) we have decreased the duration of intervention for endpoint assessment from 12 to 10 weeks. In this modification, we are changing the duration of treatment back to 12 weeks to align with what was done in the first Stage of the study, and we are changing the randomization ratio to 2:1 for nitrite relative to placebo, for the reasons enumerated below.

In the first Stage of the study, nitrite/placebo was administered in an inhaled formulation. However during the enrollment period, development of this product was discontinued by the manufacturer. In order to test the primary study hypotheses, we have switched from an inhaled formulation of nitrite to an oral formulation that achieves similar pharmacokinetics for Stage 2 of the study.

Since that time, the research pharmacy that was compounding our study drug (Triangle Pharmacy) has ceased production, forcing us to identify and work with a new pharmacy (RXQ) which has

introduced a very large delay because of the longer start up process, and the need for additional batch testing. After one shipment was received, RXQ Pharmacy failed to deliver further shipments of study drug and has not met production requirements, forcing us to again change the compounding pharmacy to The University of Iowa Pharmaceuticals (Iowa City, Iowa; uip.pharmacy.uiowa.edu). Potency and stability testing will be performed at University of Pittsburgh laboratories prior to release of study drug batches

We had planned to enroll another 68 patients, 34 receiving oral nitrite and 34 receiving oral placebo. However, we cannot meet this goal in two years. Our revised plan to meet our recruitment goal will be to use the data from the 17 patients receiving inhaled placebo in the first phase of the study. We will then combine these data with that from patients receiving oral placebo drug moving forward. Because we do not expect the response to inhaled and oral placebo to differ, we feel that this is scientifically justified.

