5.9.4 Return or Destruction of Study Drug

Participants are instructed to return all used, partly used and unused trial product at the 12 week visit (4, 8 and 12 week visit for Stage I, which has been completed). Returned trial product(s) (used, partly used or unused including empty packaging material) must be stored separately from the non-allocated trial product(s) until drug accountability has been reconciled. The investigators will keep track of all received, used, partly used and unused trial products.

6 Study Procedures

6.1 Screening Visit 1

At Visit 1, patients will provide written informed consent followed by history and physical examination performed by a cardiologist. Medications will be documented. Participants will complete a blood draw in the CRTU where (NT-proBNP levels, blood methemoglobin, blood sulfhemoglobin, fasting blood glucose and insulin levels will be tested. An optional blood collection drawing an additional 20mL's of whole blood will be collected, separated into serum and plasma by the CRTU and stored by BAP. This will be done at both the screening and final visits and stored for additional testing. We are storing the blood for future analysis and will be examining circulating inflammatory biomarkers, adipokines and how they relate to adipose tissue and HFpEF symptom severity. Assays to be run at a later date will include (subject to change): C-reactive protein (C-RP), Interleukin-3 (IL-1 β), Interleukin 6 (IL-6), Leptin, and Adiponectin. Assessment of endothelial function, baseline echocardiography, dual energy X-ray absorptiometry (DEXA) and a QOL assessment consisting of the KCCQ and SF 36 will be performed. Maximal effort cardiopulmonary exercise testing with expired gas analysis will then be performed with simultaneous echocardiography. Borg symptom severity (effort and dyspnea scores) will be recorded during standardized exercise training at a common objective workload, 2 mph on treadmill at 2° grade for 5 minutes.

Following visit 1 assessments, subjects will be instructed on the use of accelerometer (AXM) devices and devices will be dispensed. Participants are to wear AXM at all times starting at Visit 1. Participants will be randomized in a double-blind fashion at the time but will not start active treatment, and study drug will not be dispensed until the first ET visit (below).

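### The primary test of change in peak VO2 leaves out baseline peak VO2, a covariate already collected and already chosen; adding it would usually raise power but would not cure the pooling of Stage I placebo

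*Combined protocol and SAP*

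**What the plan says.** The Study Summary states: "Primary hypotheses will be tested using a two-sample t-test on the change (baseline to 12 week"). Section 7.3 sets this out as a regression of change in peak VO2 on a treatment indicator and notes that it amounts to a t-test. Covariates come in only afterwards: "we will conduct an a priori sensitivity analysis that will adjust for baseline Peak" VO2, BMI, sex and age group. The stated reason is that imbalance may arise in a small trial. The purpose of the comparison is then given as: "The type III estimate of the treatment effect will be compared to the unadjusted estimate to assess the robustness of the randomization process".

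Baseline peak VO2 is measured at Screening Visit 1 (section 6.1): "Maximal effort cardiopulmonary exercise testing with expired gas analysis will then be performed with simultaneous echocardiography".

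Two further statements bear on the point. The sample-size section builds the 68 complete patients by combining those "receiving inhaled placebo in Stage I (n=17) with another 51 patients in Stage II", so half of the 34 placebo patients come from the earlier stage. Section 1.0 defends this as follows: "Because we do not expect the response to inhaled and oral placebo to differ, we feel that this is scientifically justified". The Study Summary also says "Testing will be stratified by route of administration", but section 7.3 contains no such term.

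**The concern.** A change score fixes the slope of week-12 peak VO2 on baseline at 1. Analysis of covariance estimates that slope, and under randomisation it usually gives a smaller standard error from the same patients. The plan gives the reason to adjust (small numbers, possible imbalance) and names the covariate, yet leaves the decisive p-value unadjusted. At stake is power in a trial that was redesigned because it could not recruit enough patients. Protection against chance baseline imbalance is part of this same gain, not an additional one.

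The sentence on the randomisation process is a separate error. The gap between adjusted and unadjusted estimates reflects how far the arms happen to differ on the covariates and how prognostic those covariates are. With Stage I placebo pooled it can also reflect systematic differences between stages. It says nothing about how allocation was done. A reader could take close agreement as evidence of sound allocation for a comparison that is only partly randomised.

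**Working it through.** **Inputs from the documents (sections 7.2 and 7.3).** Difference 1.5 ml/kg/min; two-sided alpha 0.05; 34 v 34 complete patients; SD of change 2.2 (earlier exercise-training trial) or 2.0 (the trial whose figure was obtained "with placebo in subjects with HFpEF treated for 6 months was" 0).

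**Assumptions not in the documents.** The correlation rho between baseline and week-12 peak VO2; the ratio k of week-12 SD to baseline SD; and, for the main table, all 68 patients treated as randomised together.

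**The plan's own figure.** n = 2(1.960 + 0.842)² × 2.2² / 1.5² = 33.8, so 34 per group, as stated. The noncentral t with 66 df gives 79.1% power at 34 v 34. SD 2.0 would have needed only 28 per group by the same formula, so 2.2 is the SD the plan used.

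**Adjusted model.** With baseline SD s:

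- variance of change = s²(1 + k² − 2·rho·k)
- residual variance given baseline = k²s²(1 − rho²)
- at k = 1 the ratio of the second to the first is (1 + rho)/2

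At rho 0.7 and k = 1 the ratio is 0.85, and the residual SD is 2.2 × √0.85 = 2.03. Power uses the noncentral t with N − 3 df, averaged over the chance baseline difference between arms (variance factor 1 + F/(N − 2), with F distributed as F(1, N − 2)).

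| Setting | Unadjusted | rho 0.5 | rho 0.7 | rho 0.9 |
|---|---|---|---|---|
| 34 v 34, SD 2.2, k = 1 | 79.1% | 88.7% | 84.6% | 80.5% |
| 34 v 34, SD 2.2, k = 1.1 | 79.1% | 86.0% | 81.7% | 78.5% |
| 34 v 34, SD 2.0, k = 1 | 86.1% | 93.7% | 90.6% | 87.3% |
| 34 v 17, SD 2.2, k = 1 | 61.4% | 72.9% | 67.5% | 62.7% |

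In the first row the implied baseline SDs are 2.20, 2.84 and 4.92. The gain disappears at rho 0.9 when the week-12 SD is about 5% larger than the baseline SD (79.05%), and at rho 0.8 when it is 15% larger (79.0%). If baseline explains nothing of change, adjusted power is 78.5%, a loss of 79.1 − 78.5 = 0.6 points.

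The last row applies if stratification by route governs. With no Stage I nitrite patients in the analysis, the inhaled stratum holds placebo only and adds nothing to a stratified contrast, which leaves 34 nitrite v 17 placebo.

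**Effect of pooling.** Take rho 0.7, k = 1, and Stage I placebo patients whose mean baseline differs by 1 ml/kg/min from Stage II. The placebo group's mean baseline then moves by 17/34 × 1 = 0.5. The slope of change on baseline is 0.7 − 1 = −0.3, so the quantity at issue is 0.3 × 0.5 = 0.15 ml/kg/min. Which method carries it depends on why the stages differ. Simulation (40,000 trials) gave:

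| Why the stages differ | Stage I baseline | Bias, change score | Bias, adjusted | Power, change score | Power, adjusted |
|---|---|---|---|---|---|
| One baseline–outcome regression for both stages | 1 higher | +0.15 | 0 | 85.9% | 84.3% |
| One baseline–outcome regression for both stages | 1 lower | −0.15 | 0 | 69.8% | 84.2% |
| Difference stable over time | 1 higher | 0 | −0.15 | 79.4% | 76.3% |
| Difference stable over time | 1 lower | 0 | +0.15 | 79.1% | 90.3% |

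The biased method's type I error was 5.7–5.8% for the change score and 5.9% for the adjusted model. Higher power in a row with positive bias is not a real advantage. A stage difference in the change itself that baseline does not explain, of size d, biases both methods by about d/2.

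**The case against.** The strongest reply is that this is a choice of efficiency, not a mistake. The t-test on change is prespecified, matches the stated hypotheses and is what the sample size was built on, and the adjusted estimate will be reported anyway. All of that is true, and it is why the point is a recommended change rather than an essential one. The sensitivity model still leaves the primary p-value where it was.

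The size of the gain rests on rho and the SD ratio, neither of which the documents give. At rho 0.9 with equal SDs it is only 80.5 − 79.1 = 1.4 points, and it can become a small loss. This stands, so the range matters more than the 84.6%.

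Pooling also means that the fully randomised 34 v 34 calculation does not describe this trial exactly, and adjustment can introduce bias where the change score has none. That stands too, but the reverse case is equally possible and the documents do not show which applies, so pooling gives no reason to prefer the change score.

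For a 34 v 17 contrast the worst-case loss is slightly larger: 61.4% falls to 60.5% if baseline explains nothing of change.

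The sentence about randomisation drives no decision rule, so it is a matter of wording; it is nevertheless wrong as written. The separate SAP to which the protocol refers was not in the supplied text, but the protocol says that it gives the primary analysis itself, so section 7.3 has to be right in its own terms.

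**Conclusion.** The concern holds. The primary test is valid but forgoes a covariate that is measured at screening and already named in the plan. With SD of change 2.2, equal SDs and 34 v 34 treated as fully randomised, power would rise from 79.1% to between 80.5% and 88.7% for rho from 0.9 down to 0.5 (84.6% at 0.7). The gain shrinks or vanishes if the week-12 SD exceeds the baseline SD and rho is high. The cost under full randomisation is at most about 0.6 points. These figures depend on a correlation and an SD ratio that the documents do not supply, so confidence in the size of the gain is moderate.

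Baseline adjustment is not a remedy for pooling Stage I placebo. Separately, and without any numerical assumption, comparing adjusted and unadjusted estimates cannot assess the randomisation process.

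**What to change.** - In section 7.3, make the primary model change in (or week-12) peak VO2 on treatment plus baseline peak VO2, and fix it before unblinding. Align the line in the Study Summary.
- Keep the unadjusted t-test as supportive and the model that also includes BMI, sex and age group as a sensitivity analysis.
- Delete the statement that comparing the estimates assesses the randomisation process.
- Tabulate baseline peak VO2 separately for Stage I and Stage II placebo, and do not present baseline adjustment as a correction for pooling.
- Reconcile, as a separate matter, the Study Summary's stratification by route with section 7.3, which has no such term.

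The cost is one paragraph in section 7.3 and one line in the Study Summary, with no new data. The remaining risk is the pooling bias shown above, about 0.15 ml/kg/min per 1 ml/kg/min difference in baseline between stages at rho 0.7, which can fall on either method.
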